4.11.2.1. Hypoglycemia

- Percentage and Duration (in minutes) of time per day where glucose values are within a hypoglycemic range (defined as ≤ 70 mg/dL [3.9 mmol/L]) during the nighttime period (defined as midnight to 0600 hours).
- Percentage and Duration (in minutes) of time per day glucose values are within a hypoglycemic range (defined as ≤ 70 mg/dL [3.9 mmol/L]) during a 24-hour period.
- Percentage and Duration (in minutes) of time per day where glucose values are within a hypoglycemic range (defined as < 54 mg/dL [3.0 mmol/L]) during the nighttime period.
- Percentage and Duration (in minutes) of time per day where glucose values are within a hypoglycemic range (defined as < 54 mg/dL [3.0 mmol/L]) during a 24-hour period.
- Incidence of hypoglycemic episodes during the nocturnal period and during a 24-hour period.
- Rate of hypoglycemic episodes per patient per year during the nighttime period and during a 24-hour period.
- Duration (in minutes) of each individual hypoglycemic episode.

4.11.2.2. Hyperglycemia

- Percentage and Duration (in minutes) of time per day glucose values are within a hyperglycemic range (defined as > 180 mg/dL [10.0 mmol/L]) during a 24-hour period.

4.11.2.3. Normal Range

- Percentage and Duration (in minutes) of time per day glucose values are within a normal glycemia range (defined as between 71 mg/dL and 180 mg/dL [3.9 and 10.0 mmol/L]) inclusive during a 24-hour period.
- Percentage and Duration (in minutes) of time per day glucose values are within a normal glycemia range (defined as between 71 mg/dL and 140 mg/dL [3.9 and 7.8 mmol/L]) inclusive during a 24-hour period.

4.11.2.4. Glycemic Variability

- Low Blood Glucose Index (LBGI) during the nighttime period and during a 24-hour period.
- High Blood Glucose Index (HBGI) during the nighttime period and during a 24-hour period.
- Combined blood glucose risk index (derived as LBGI + HBGI) during the nighttime period and during a 24-hour period.
- Within-day and between-day glucose coefficient of variation during the nighttime period and during a 24-hour period.
- Within-day and between-day glucose SD during the nighttime period and during a 24-hour period.

4.11.3. Definition of Variables

In this section, we define the derived variables that are used for the analysis in Section 4.11.2 and some additional variables that may be used for exploratory analyses.

4.11.3.1. Glucose in Target Ranges, Hypoglycemia or Hyperglycemia

The percentage of time within a glucose range (target, hypoglycemia or hyperglycemia ranges) will be calculated as the number of observations within the specified range divided by the number of observations in the time interval (for example, 24-hour period). The duration (in minutes) within the glucose range will then be calculated as the percentage of time within the glucose range times the length of the period (24 hour, 18 hour, and 6 hour, for the periods of 24 hour, daytime or nighttime, respectively).

4.11.3.2. Hypoglycemic Episode

The CGM-determined hypoglycemic episode is defined as ISIG meeting the hypoglycemia range (e.g., <54 mg/dL or ≤ 70 mg/dL) for at least 15 minutes and the end of a hypoglycemic episode is defined as the absence of sensor readings ≥ 54 mg/dL for 15 minutes or more. The linear interpolation method will be used to determine the start/end time when the patient's glucose value crossed the glucose threshold.

The duration of each episode will be calculated using the time difference between the 2 time points before the incidence starts and after the incidence ends.

The CGM-determined nighttime hypoglycemic episode is defined as hypoglycemic episodes that occur between 2400 hours and 0600 hours. To calculate the duration of nighttime hypoglycemic episode, the end date/time will be the end date/time when the patient passes outside the hypoglycemic range even if it is outside the interval of 2400 hours and 0600 hours.

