3.3. Exploratory Objectives

1. Fasting serum glucose (FSG) by laboratory and change from baseline to Weeks 6, 12, 18, and 32 and all other scheduled visits;
2. Fasting blood glucose (FBG) by self-monitored blood glucose (SMBG) and change from baseline at Weeks 12 and 32 and all other available visits;
3. Fasting blood glucose (FBG) intra-patient variability (by SMBG) at Weeks 12 and 32 and all other available visits;
4. Six-point SMBG profile (pre-meal and 2-hour postprandial SMBG measurements for the morning, midday, and evening meals in 1 day.) at Visit 6, 9, 12, 15, 17, 20, 21;
5. Proportion of patients with HbA1c <7.0% at 12 and 32 weeks;
6. Proportion of patients with HbA1c \leq 6.5% at 12 and 32 weeks;
7. Triglycerides, free fatty acid (FFA), liver aminotransferase (alanine aminotransferase [ALT]/aspartate aminotransferase [AST]) change from baseline to Weeks 6, 12, and 32;
8. Discontinuation of investigational product (IP) due to AEs;
9. Clinical laboratory results;

10. Number of dose adjustments to steady-state;
11. Antibodies to LY3209590;
12. Incidence and rate of documented non-nocturnal hypoglycemia during the treatment period (0-12, 12-32, and 0-32 weeks);
13. Incidence and rate of hypoglycemia during the treatment period (0-12, 12-32, and 0-32 weeks) by continuous glucose monitoring (CGM);
14. Glucose time in target range, time in hyperglycemia, time in hypoglycemia during the treatment period (0-12, 12-32, and 0-32 weeks) by CGM;
15. Total cholesterol, low-density lipoprotein cholesterol (LDL-C), high-density lipoprotein cholesterol (HDL-C) and change from baseline to Weeks 6, 12, and 32.

4. A Priori Statistical Methods

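### CGM hypoglycemic episodes start at <54 or ≤70 mg/dL but share one end rule at 54 mg/dL, so ≤70 episodes cannot be correctly ended, timed or counted from the SAP text

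*SAP*

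**What the plan says.** SAP 4.11.3.2 starts a CGM episode on "ISIG meeting the hypoglycemia range (e.g., <54 mg/dL or ≤ 70 mg/dL) for at least 15 minutes". The same sentence then gives one end rule for both ranges: "the end of a hypoglycemic episode is defined as the absence of sensor readings ≥ 54 mg/dL for 15 minutes or more".

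Three further statements in that section bear on timing:

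- Start and end times are found by linear interpolation, at the point where the "glucose value crossed the glucose threshold". The section does not say which threshold.
- Duration is calculated "using the time difference between the 2 time points before the incidence starts and after the incidence ends".
- For the duration of nighttime episodes only, "the end date/time will be the end date/time when the patient passes outside the hypoglycemic range", even if that falls after 0600 hours.

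SAP 4.11.2.1 plans two outputs that need an episode end: "Rate of hypoglycemic episodes per patient per year during the nighttime period and during a 24-hour period" and "Duration (in minutes) of each individual hypoglycemic episode". SAP 3.3 lists the CGM rate among the exploratory objectives: "Incidence and rate of hypoglycemia during the treatment period (0-12, 12-32, and 0-32 weeks) by continuous glucose monitoring (CGM").

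**The concern.** There are two separate faults.

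**Threshold.** An end value of 54 mg/dL can suit only the <54 episode. For a ≤70 episode, every reading from 54 to 70 is inside the defining range. With the direction corrected, the same reading also counts as recovered. An episode that stays in that band has no 54 mg/dL crossing by which to time its end.

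**Direction, if the sign is as printed.** An absence of readings at or above 54 means that glucose has stayed below 54. A ≤70 episode that never falls below 54 then has no end, and for a <54 episode the end condition repeats the start condition.

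What is at stake is the CGM episode rate (nighttime and 24-hour) and the 24-hour duration per episode. Protocol 3.2 names more frequent or longer hypoglycemic events as the possible drawback of so long-acting an agonist, and these outputs speak directly to that. Protocol Table BDCM.2 also lists recurrence of events as an exploratory endpoint. It is touched only so far as it needs episode ends, since the SAP derives no recurrence variable.

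**Working it through.** The documents give no figure for CGM episodes, so there is nothing to reproduce. The check applies the text to simple constructed traces, which are assumptions and not trial data.

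**Inputs.** Sampling every 5 minutes (SAP 4.11.1); start ranges and the 15-minute requirement (SAP 4.11.3.2). Each trace sits at 110 mg/dL, with one reading of 80 on each side of the low; the first 80 is at minute 120. Results are the same whether 15 minutes means 3 or 4 readings, and whether or not a new episode requires leaving the range first, except where stated.

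**End rules compared.** (i) As printed: all readings <54 for 15 minutes. (ii) Direction corrected, 54 kept: all readings ≥54 for 15 minutes. (iii) Exit from the defining range for 15 minutes: >70 for ≤70 episodes, ≥54 for <54 episodes.

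**Crossing time.** Between consecutive readings g1 (at t1) and g2, threshold T is crossed at t1 + 5 × (g1 − T)/(g1 − g2).

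**Trace A, 60 minutes at 60 (13 readings, minutes 125 to 185), ≤70 episode**
- Start: 120 + 5 × (80 − 70)/(80 − 60) = 122.5. End: 185 + 5 × (60 − 70)/(60 − 80) = 187.5.
- Rule (iii): one episode of 187.5 − 122.5 = 65.0 minutes.
- Rule (ii): the end condition is met at the first in-range reading (minute 125), and no 54 crossing exists within the low. The count is 1 if a new episode requires leaving the range. With immediate re-entry it is 4 (3-reading windows) or 3 (4-reading windows). It is 2 if 4-reading windows are used, the end is sought only once the start is confirmed, and end windows are used up before the next start.
- Rule (i): the episode never ends.

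**Trace B, the same low twice, about 3 hours apart**
- Rule (iii): two episodes of 65.0 minutes. Rule (i): one open episode.

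**Trace C, 30 minutes at 50, then 120 minutes at 60 (7 and 25 readings), ≤70 episode**
- Start: 120 + 5 × (80 − 70)/(80 − 50) = 121.67.
- Rule (iii) end: 280 + 5 × (60 − 70)/(60 − 80) = 282.5. Duration 282.5 − 121.67 = 160.8 minutes.
- Rule (ii) end: 155 + 5 × (50 − 54)/(50 − 60) = 157.0. First episode 157.0 − 121.67 = 35.3 minutes, ending with glucose still at 60.
- Coded as 6 and 24 readings, the figures are 150.8 and 30.3 minutes.

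**Trace D, 60 minutes at 50 (13 readings), <54 episode**
- Start: 120 + 5 × (80 − 54)/(80 − 50) = 124.33. End: 185 + 5 × (50 − 54)/(50 − 80) = 185.67.
- Rules (ii) and (iii) coincide: 185.67 − 124.33 = 61.3 minutes.
- Rule (i): the end condition is met at the first reading.

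Correcting the direction therefore repairs the <54 definition but leaves the ≤70 definition wrong.

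**Duration sentence (minor).** If it means the outer readings, trace A lasts 190 − 120 = 70 minutes against 65.0 by interpolation. At 5-minute sampling the two differ by 0 to 10 minutes per episode.

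**The case against.** The strongest reply is that the intent is clear. Nighttime episodes are a subset of all episodes, and for them the end is exit from the range. Start and end are timed at a threshold crossing, and the end clause already gives a 15-minute persistence requirement. Read together, these suggest a single rule, exit from the defining range, with a slip in the printed value and sign. It can be added that SAP 4.11.2.1 names no threshold for episode rate or duration, that the split counts depend on coding, and that a programmer working from the defining threshold would not end trace C at a 54 crossing.

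Much of this stands. Exit from the range is the likely intent, the direction may be a slip or a misread sign, the counts do vary with coding, and the outputs are exploratory.

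It does not remove the fault. The favorable reading has to override the only recovery rule the section states. It does so with a sentence written for nighttime duration and a threshold left unnamed. Neither sentence says how long recovery must last before a further low is a new episode, which the rate needs; the sentence that does say so uses 54. A programmer who ends trace C at 70 is not applying that sentence. If only <54 episodes are reported, the printed end condition still repeats the start. The spread in counts shows that programmers following this text could get different rates from the same data.

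**Conclusion.** The concern holds and should be fixed. The single 54 mg/dL end threshold fails for ≤70 episodes under either reading of the sign. The inverted direction is a further fault if the sign is as printed.

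Not affected: nighttime episode duration, which has its own end; incidence over the whole period, which needs only the start rule; time in range, which counts readings (SAP 4.11.3.1); reported hypoglycemia (SAP 4.10.3.2); and HbA1c. One rule applies to all three arms, so no bias between arms is claimed.

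The sizes shown, such as 35.3 against 160.8 minutes, are illustrations. A trial-level figure would depend on the coding and on how long glucose stays between 54 and 70, so none is given. No derivation program is available, so the conclusion concerns the text only.

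**What to change.** Replace the end rule in SAP 4.11.3.2 with wording to this effect: an episode at a given threshold ends at the start of the first run of at least 15 consecutive minutes outside the range that defines it (≥54 mg/dL for <54 episodes, >70 mg/dL for ≤70 episodes); a new episode can start only after that; start and end times are the linearly interpolated crossings of that same threshold, and duration is the difference between them. Apply it to nighttime and 24-hour episodes alike, and align the existing duration sentence with it. Check the printed sign against the signed PDF.

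The cost is a few sentences in one SAP section and one change in the derivation program. No new data are needed.

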**Table BDCM.2. Objectives and Endpoints**

Objectives	Endpoints
Primary 
 
To investigate the efficacy of LY3209590 arms in study participants with T2DM
 
	
 
HbA1c change from baseline to Week 32
 

Secondary Efficacy 
 
To investigate the efficacy of LY3209590 compared with insulin degludec in study participants with T2DM.
 
	
 
HbA1c change from baseline to Week 12 and 32
 
Fasting glucose change from baseline to Weeks 12 and 32
 
Insulin dose change from baseline to week 12 and 32
 

Safety 
 
To investigate the safety of LY3209590 compared with insulin degludec in study participants with T2DM.
 
	
 
Incidence and rate of hypoglycemia
 
Incidence and rate of nocturnal hypoglycemia
 
Incidence and rate of severe hypoglycemia
 
Incidence of treatment-emergent serious AEs
 
Body weight change from baseline at Weeks 12 and 32
 

Pharmacokinetics 
 
To characterize the PK of LY3209590 in study participants with T2DM
 
	
 
LY3209590 population-based parameters, such as, AUC within dosing interval at Weeks 12 and 32
 

Exploratory 
 
To investigate the safety and tolerability of LY3209590 compared with insulin degludec in study participants with T2DM.
 
	
 
Treatment-emergent AEs
 
Discontinuation of IP due to AEs
 
Clinical laboratory results
 
Systematic assessment of injection site reactions
 
Insulin dose during follow up period
 
Incidence and rate of hypoglycemia during treatment and follow-up period
 
Incidence and rate of daytime hypoglycemia
 
Liver aminotransferase change from baseline to Weeks 12 and 32
 

 
To explore quality of glycemetic control compared with insulin degludec using CGM
 
	
 
Glucose time in target range, time in hyperglycemia, time in hypoglycemia
 
Duration and recurrence of hypoglycemic events
 

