4.11. Continuous Glucose Monitoring Analysis

4.11.1. General Consideration

The continuous glucose monitoring system will be offered to all patients at selected sites in Study I8H-MC-BDCM. Interstitial glucose (ISIG) values will be collected by the CGM at 5-minute intervals. Continuous glucose monitoring recordings will be obtained for all patients throughout the treatment phase of the study. The device readings and alarms will not be blinded to the patients so that they can be warned of hypoglycemia and appropriately manage any hypoglycemic episodes.

All patients who are randomized to 1 of the study treatments (LY3209590 Algorithm 1, LY3209590 Algorithm 2, insulin degludec) receive at least 1 dose of study treatment, and have CGM data from at least 1 collection period which will be included in the analyses. The data collected after permanent discontinuation of investigational product will be censored. There will be no multiplicity adjustment. Since the sensor takes about 2 hours to reach the steady state after insertion, it is recommended to only use the steady state data for analysis.

Summary statistics will include the number of observations, mean, median, maximum, minimum, and SD for all continuous measures. For categorical measures, the number of observations, proportion, and frequencies will be included in summary statistics. All analyses will be performed for data collected by visit and treatment.

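### SAP 4.11.3.2 times CGM hypoglycemic episodes by interpolated crossings in one sentence and by bracketing readings in the next, so recorded durations can differ by 0 to 10 minutes per episode

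*SAP*

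**What the plan says.** SAP 4.11.1 fixes the sampling: "Interstitial glucose (ISIG) values will be collected by the CGM at 5-minute intervals". SAP 4.11.3.2 then requires glucose to stay in the hypoglycemic range (<54 or ≤70 mg/dL are its examples) for 15 minutes or longer before a run counts as an episode. It does not say how those 15 minutes are clocked.

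The same section makes three statements about timing:

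- Start and end: "The linear interpolation method will be used to determine the start/end time when the patient's glucose value crossed the glucose threshold".
- Duration of each episode: "The duration of each episode will be calculated using the time difference between the 2 time points before the incidence starts and after the incidence" has ended.
- Nighttime episodes: "the end date/time will be the end date/time when the patient passes outside the hypoglycemic range", even if that falls after 0600.

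The notation in SAP 4.11.3.3 uses the term time point for a sampled glucose value. SAP 4.11.2.1 lists the duration of each individual episode, and the incidence and rate of episodes, as variables to be compared between arms. Protocol Table BDCM.2 lists "Duration and recurrence of hypoglycemic events" under the exploratory objectives.

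On gaps, SAP 4.11.1 notes: "Since the sensor takes about 2 hours to reach the steady state after insertion", and recommends analyzing only steady-state data. SAP 4.11.2 acknowledges lost CGM records when visits are more than 4 weeks apart. Section 4.11.3.2 has no rule for an episode that adjoins a gap.

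**The concern.** A threshold crossing is itself the start or end of an episode. A point before the start or after the end is something else, and given how 4.11.3.3 uses the term, it is most naturally the neighboring sensor reading. Those neighbors are outside the hypoglycemic range by definition, so the duration sentence read literally adds time when the participant was not hypoglycemic. The nighttime sentence goes back to the crossing, so nighttime and 24-hour episodes could be ended by different rules.

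Protocol 3.2 names longer-lasting hypoglycemia as a possible downside of a very long-acting insulin, and the trial uses CGM to watch for it. A reader of the results will therefore look at the absolute length of episodes, and that length depends on which sentence is programmed. The study is open-label and SAP 4.13 provides for routine unblinded reviews, so the choice is better fixed in writing than left to programming.

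**Working it through.** The SAP states no numeric duration, so there is no figure of its own to reproduce. The check is arithmetic on the 5-minute grid.

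**Inputs**

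- Sampling interval: 5 minutes (SAP 4.11.1).
- Minimum time in range: 15 minutes (SAP 4.11.3.2).
- k: number of consecutive in-range readings.
- a: minutes from the entry crossing to the first in-range reading. b: minutes from the last in-range reading to the exit crossing. Each lies between 0 and 5.
- Where the crossing falls within its interval: not in the documents. I assume a uniform position for averages and also show the full range.

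**Formulas**

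- Interpolated duration: A = 5(k−1) + a + b
- Bracketed duration: B = 5(k+1)
- Difference: B − A = 10 − (a + b)

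Since a + b lies between 0 and 10, the difference lies between 0 and 10 minutes and is never negative. With uniform crossings its mean is 10 − 2.5 − 2.5 = 5.0 and its SD is √(2 × 25/12) = 2.04. In a second check with 200,000 simulated parabolic dips (dip length 5–60 minutes, depth 1–15 mg/dL, random phase; all assumed), the mean was 5.4.

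**Worked traces, threshold <54 mg/dL**

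| Readings (mg/dL) | k | A (min) | B (min) | B − A |
|---|---|---|---|---|
| 60, 52, 50, 57 | 2 | 5 + 1.25 + 2.86 = 9.1 | 15 | 5.9 |
| 54, 50, 50, 54 | 2 | 5 + 5 + 5 = 15.0 | 15 | 0 |
| 56, 53, 50, 52, 57 | 3 | 10 + 1.67 + 2.00 = 13.7 | 20 | 6.3 |
| 60, 53, 50, 53, 60 | 3 | 10 + 0.71 + 0.71 = 11.4 | 20 | 8.6 |
| 55, 48, 47, 48, 55 | 3 | 10 + 4.29 + 4.29 = 18.6 | 20 | 1.4 |

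**The 15-minute minimum under each clock**

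| k | A (min) | Meets 15 under A | B (min) | Meets 15 under B |
|---|---|---|---|---|
| 1 | 0–10 | no | 10 | no |
| 2 | 5–15 | only in the limiting case | 15 | yes |
| 3 | 10–20 | 50% (uniform), 40% (parabolic) | 20 | yes |
| 4 | 15–25 | yes | 25 | yes |

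The limiting case for k = 2 needs both neighbors exactly at 54, which is possible because 54 is outside a <54 range. It cannot occur for ≤70, where a neighbor at 70 would itself be in range.

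**Gaps.** If the interval at one end of the episode is a gap of G minutes, bracketing adds all of G and interpolation adds some fraction of it. The difference at that end is then 0 to G rather than 0 to 5.

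**Between-arm contrast.** SAP 4.11.2 plans LS mean differences. In the parabolic check the mean offset was 5.85, 5.55 and 5.43 minutes for k = 2, 3 and 4. It moves by only about 0.4 minutes with episode length, so most of it cancels when one arm is subtracted from another.

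**The case against.** The strongest reply is that the duration sentence is loose wording. Two of the three timing statements point to the crossing, so a programmer has a majority reading to follow, and the two time points may have been meant as the interpolated start and end. That is possible, but the words describe points outside the episode, and a plan approved before database lock should not need a majority vote.

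Two stronger readings are tempting, and the documents do not support them.

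- A reader might infer that every duration shifts by a fixed 5 minutes. It does not: the traces above differ by 0 to 8.6 minutes, and 5 is only an average under an assumed crossing position.
- A reader might infer that the two sentences by themselves change which episodes count. The duration sentence applies to episodes already identified, and bracketed time is partly out of range, so nothing in the text ties it to the 15-minute minimum. What the SAP leaves open is how that minimum is clocked. If interpolation clocks it, incidence and rate do not change.

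Nor can a whole sensor gap be charged to bracketing. The interpolation sentence has no gap limit either and would also absorb part of it. The missing gap rule affects both methods.

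Three further points stand. The endpoint is exploratory. The same rule would apply to all arms. And the end condition in 4.11.3.2 needs separate repair: it uses 54 mg/dL even for ≤70 mg/dL episodes and, read literally, describes glucose staying below 54. An interpolated end time is not fully reproducible until that is settled too.

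**Conclusion.** The conflict is real and its reach is limited. Taken literally, the duration sentence is never shorter than the interpolated time and overstates each episode's time in range by 0 to 10 minutes, and possibly by more when a gap adjoins the episode. The 0-to-10 range follows from the 5-minute grid alone. The average of about 5 minutes, one third of the 15-minute minimum, rests on uniform crossing positions (5.4 under the parabolic assumption).

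The effect on episode counts is conditional. Only if the bracketing clock were also used for the 15-minute minimum would two-reading runs go from almost never to always qualifying, and three-reading runs from roughly 40–50% to always, changing CGM incidence and rate. The SAP does not say that it would be.

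What is affected with certainty is the absolute value of CGM episode duration. Planned between-arm mean differences are largely protected. The HbA1c analyses, the diary-based hypoglycemia analyses in SAP 4.10.3.2, and CGM time in range, which SAP 4.11.3.1 derives from counts of readings, are untouched.

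**What to change.** In SAP 4.11.3.2:

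1. Delete the bracketing sentence and define duration as interpolated end time minus interpolated start time.
2. State that the 15-minute minimum is measured on the same interpolated clock.
3. Do not interpolate across a sensor gap longer than a pre-set limit. End the episode at the last reading before such a gap and, by the same logic, start it no earlier than the first reading after one. The limit is the sponsor's judgment; 15 minutes would be one choice.

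The end condition noted above should be clarified in the same edit, because the interpolated end depends on it.

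The cost is a few lines of SAP text and a small programming rule, with no new data collection. The downside is that episodes next to sensor gaps will be recorded as shorter than they may have been; reporting how many episodes adjoin a gap, by arm, would let a reader judge that.
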